#### 1.4. Preclinical findings

We observed that mTORC1 inhibition with RAD001 in ER+ breast cancer cell lines induces upregulation of PI3K/AKT signaling (Fig. 2). Pretreatment with the anti-estrogen fulvestrant (which blocks ER transcriptional activity) suppressed RAD001 -induced PI3K/AKT signaling. *IGF1R*, *IRS1*, and *IRS2* are ER-induced genes, and studies have demonstrated crosstalk between the ER and IGF-1R pathways at several levels [reviewed in (10)]. Fulvestrant treatment decreased the levels of IGF-1R, IRS-1, and IRS-2 at the protein and/or mRNA levels, which likely suppressed RAD001-induced PI3K/AKT activation. These findings suggest that continued anti-estrogen therapy would be beneficial in the context of treatment with RAD001 in patients.

Presurgical treatment with the aromatase inhibitor Letrozole for 3 days is sufficient to significantly suppress plasma estrogen levels. Gene expression profiling of pre-treatment (baseline, diagnostic biopsy) and post-two-week-treatment (surgical) ER+ tumor specimens revealed that estrogen deprivation via Letrozole induced changes in expression of ER-regulated genes. *IRS1* was one of the most significantly and consistently downregulated genes when comparing pre- and post-treatment samples. *IGF1R* was also significantly downregulated by Letrozole (11).

[figure not shown]

Fig. 2. Anti-estrogen-mediated inhibition of ER with fulvestrant abrogates PI3K/AKT activation induced by mTORC1 inhibition with RAD001. *Left:* MCF-7 cells were pre-treated with medium containing 10% FBS  $\pm$  1  $\mu$ M fulvestrant for 24 hours. Then cells were treated with medium  $\pm$  1  $\mu$ M fulvestrant  $\pm$  20 nM RAD001 for 24 hours before lysis. Lysates were analyzed by immunoblotting using the indicated antibodies. *Right:* ZR75-1 cells were pre-treated with medium containing 10% FBS  $\pm$  1  $\mu$ M fulvestrant for 3 days. Then cells were treated with medium  $\pm$  1  $\mu$ M fulvestrant  $\pm$  20 nM RAD001 for 24 hours before lysis. Lysates were analyzed as in (A). Note that RAD001 treatment decreases P-S6 (marker of mTORC1 activity) but increases P-AKT. Fulvestrant treatment decreases IRS-1 and IGF-1R levels, which are encoded by ER-inducible genes.

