### 5.4. Evaluable patients

Subjects who proceed to a definitive surgical procedure with A) tumor tissue sufficient to provide punch biopsy specimens for research purposes, and B) histologically-confirmed tumor tissue in the surgical specimen with  $\geq 50\%$  tumor cellularity, will be considered evaluable. Subjects whose surgical specimens do not contain adequate tumor tissue to assess the primary endpoint will not be considered evaluable, and will need to be replaced.

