### 5.5. Analyses

#### 5.5.1. *Ex vivo analysis of RAD001 effects on IRS-1/PI3K/AKT signaling.*

Fresh viable tumor cores in tissue culture medium (serum-free DMEM + Pen/Strep) will be placed into medium containing 20 nM RAD001 (4 cores) or DMSO control (4 cores) and cultured at 37°C for 1 hour. If extra tissue cores are available, we will treat +/- 20 nM RAD001 for 2-8 hours to evaluate delayed changes in signaling, and treat +/- 1 uM OSI-906 (IGF-1R/InsR inhibitor) for 1-8 hours to determine whether PI3K/AKT signaling is IGF-1R/InsR-dependent in these tumors. Tissue cores will then be snap-frozen in liquid nitrogen and stored at -80°C.

Immunoblotting- Two cores each of DMSO- and RAD001-treated tumor will be homogenized and lysed on ice in RIPA buffer containing protease and phosphatase inhibitors. Samples will be sonicated and centrifuged, and supernatant will be used to quantify protein concentration. Protein lysates for immunoblotting will then be mixed with reducing sample buffer and stored at -80°C. Lysates will be heated at 95°C for 1 min. just before SDS-PAGE following by immunoblot analysis using antibodies against:

IRS-1

phospho-IRS-1-Ser636/639 (marker of p70S6K activity)

IRS-2

AKT

phospho-AKT-S473 (marker of mTORC2 activity)

phospho-AKT-T308 (marker of PIP3 levels and PI3K/PDK1 activity)

4E-BP1

phospho-4E-BP1-Thr37/46 (marker of mTORC1 activity)

p70S6K  
phospho-p70S6K-Thr389 (marker of mTORC1 activity)  
S6  
phospho-S6-Ser240/244 (marker of p70S6K activity)  
phospho-S6-Ser235/236 (marker of p70S6K and RSK activity)  
Erk1/2  
phospho-Erk1/2-Thr202/Tyr204 (marker of MEK activity)  
IGF-1Rb  
InsRb

If excess protein lysate is available, we will immunoprecipitate the p85 subunit of PI3K, and immunoblot for IRS-1 and IRS-2 to assess drug induced changes in IRS-1/2-induced PI3K activation. We will also immunoprecipitate using phospho-Tyrosine antibody, and immunoblot for IGF-1Rb, InsRb, IRS-1, and IRS-2 to assess protein activation.

The primary goal of this analysis is to determine whether RAD001 treatment *ex vivo* globally decreases mTORC1 signaling (indicated by a decrease in levels of phospho-p70S6K, phospho-S6, and phospho-4E-BP1), increases IRS-1/2 levels and phosphorylation, and increases AKT phosphorylation. Secondary goals are to assess changes in IGF-1R and InsR activation, and compensatory signaling through the MEK/Erk pathway.

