Immunohistochemistry (IHC) on frozen tissues- Two cores each of DMSO- and RAD001-treated tumor will be sectioned and processed for IHC in the Pathology Translational Research Shared Resource. Tissue sections will be immunostained using antibodies against phospho-S6-Ser240/244, phospho-AKT-S473, phospho-AKT-T308 and phospho-IGF-1Rb/InsR- Tyr1131/Tyr1146. Samples will be scored using a Histoscore scale that incorporates staining intensity and frequency (12).

The primary goal of this analysis is to determine whether RAD001 treatment *ex vivo* decreases mTORC1 signaling (indicated by a decrease in levels of phospho-S6) and increases AKT phosphorylation uniformly throughout tumor cores, and whether drug treatment alters IGF-1R/InsR phosphorylation (which cannot be assessed by immunoblot analysis of protein lysates). Staining intensities in the center of each core will be compared to the outer edges to assess uniformity of signal; non-uniformity may be due to time of exposure of cells to drug or medium.

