alter IRS-1/PI3K/AKT pathway activation in breast tumors. RAD001-induced pathway activation will be defined as a  $\geq 50\%$  increase in phospho-AKT densitometric signal value compared to DMSO-treated control; this scoring system provides a binary metric for sample size determination for Arm B (below). Given that this is a pilot study, we do not know what fraction of ER+/HER2-breast tumors will exhibit RAD001-induced IRS-1/PI3K/AKT activation. Hence, tumors from 10 untreated patients in Arm A will be used to determine the frequency with which RAD001 induces AKT activation.

The fraction of tumors in Arm A (untreated patients) that exhibit RAD001-induced AKT activation will be used to determine the number of patients that need to be enrolled in Arm B (presurgical Letrozole treatment) to detect a significant effect of presurgical Letrozole treatment on RAD001-induced AKT activation. We estimate that  $\leq 15\%$  of Letrozole-treated tumors will exhibit RAD001-induced AKT activation. If we observe that RAD001 increases phospho-AKT in X of 10 tumors in Arm A, we will enroll Y patients in Arm B (presurgical Letrozole) to provide a sufficient number of tumors to detect a significant effect ( $p \leq 0.05$ ) of presurgical Letrozole on RAD001-induced changes in phospho-AKT levels with 80% power (calculated using uncorrected chi-squared statistic). If we observe that  $\leq 3$  tumors from untreated patients in Arm A exhibit RAD001-induced AKT activation, the study will be terminated at this point, and Arm B will not enroll patients. To account for interpatient/intertumor variability, we will enroll a minimum of 10 patients in Arm B.

X (n of tumors from untreated patients that exhibit a <math>\geq 50\%</math> increase in P-AKT levels in response to RAD001 treatment ex vivo)	Y (n of patients to be enrolled in Arm B, presurgical Letrozole)
0-3	Terminate study
4-6	30
7-8	14
9-10	10

- 10.

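### The Arm A stop rule scores tumors on phospho-AKT alone, so tumors in which RAD001 never inhibited mTORC1 count as non-activated and can end the study or enlarge Arm B

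*Combined protocol and SAP*

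**What the plan says.** Section 9.6 defines RAD001-induced activation as a 50% or greater "increase in phospho-AKT densitometric signal value compared to DMSO-treated control; this scoring system provides a binary metric for sample size determination for Arm B". It adds that "tumors from 10 untreated patients in Arm A will be used to determine the frequency with which RAD001 induces AKT activation". That count, X, drives two decisions. If three or fewer "tumors from untreated patients in Arm A exhibit RAD001-induced AKT activation, the study will be terminated at this point". Otherwise X sets the Arm B size: 30 for X of 4 to 6, 14 for 7 to 8, and 10 for 9 to 10, on the expectation that at most 15% "of Letrozole-treated tumors will exhibit RAD001-induced AKT activation".

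Section 5.4 takes as evaluable "Subjects who proceed to a definitive surgical procedure with A) tumor tissue sufficient to provide punch biopsy specimens for research purposes" and, in addition, at least 50% tumor cellularity. It sets no condition on what the drug did in culture.

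Section 5.5.1 describes the assay. 1-mm cores are placed in 20 nM RAD001 or DMSO and "cultured at 37°C for 1 hour". The immunoblots include phospho-p70S6K, phospho-S6 and phospho-4E-BP1, and a fall in these is part of the stated primary goal of that analysis. The IHC part compares core centers with edges because "non-uniformity may be due to time of exposure of cells to drug or medium". The supporting cell-line work in Section 1.4 used "20 nM RAD001 for 24 hours before lysis".

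Section 9.3 compares the magnitude of change between arms with a two-sided independent t-test.

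**The concern.** Primary objective 1 (Section 2.1) is conditional: does inhibiting mTORC1 raise IRS-1/PI3K/AKT activation? A tumor in which mTORC1 was not inhibited ex vivo, because drug did not reach the cells or the core was not viable, carries no information on that question. The laboratory will know which tumors these are, because the mTORC1 markers are read on the same lysates. No rule uses that knowledge. Section 5.2 opens Arm B after the molecular analyses have been successfully completed, but does not say that success includes confirmed mTORC1 inhibition.

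At stake first is a termination that could reflect absent feedback or an assay that did not work. Short of termination, a deflated X moves the trial to a larger Arm B row, so more patients take presurgical Letrozole than the design intended. The between-arm comparison is affected too, in a different and weaker way.

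**Working it through.** **Inputs.** From Section 9.6: Arm A n = 10, stop at X ≤ 3, Arm B sizes 30, 14 and 10, Arm B rate 15%, uncorrected chi-squared, 80% power. From Section 9.5: two-sided 0.05. Assumed, because the documents give neither: the true activation rate p among tumors with mTORC1 inhibited, and the share q of tumors not inhibited, none of which is taken to show a 50% phospho-AKT rise.

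**1. The plan's own figure.** Exact enumeration of the uncorrected chi-squared test, Arm A n = 10 with rate X/10 against 15% in Arm B, gives power of 79.6% (X = 6, Y = 30), 80.5% (X = 7, Y = 14), 93% (X = 8, Y = 14) and 97% (X = 9, Y = 10). These agree with the plan's 80% or exceed it. X = 4 and X = 5 with Y = 30 give 39% and 61%; that is a separate matter and nothing below depends on it. The table takes X/10 as the activation rate and leaves no room for failed assays. The plan states no operating characteristics for the stop rule.

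**2. Stop rule.** X ~ Binomial(10, p(1 − q)), and P(stop) = P(X ≤ 3).

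- p = 0.5, q = 0: (1 + 10 + 45 + 120)/1024 = 176/1024 = 17.2%.
- p = 0.5, q = 0.2, so rate 0.40: 0.0060 + 0.0403 + 0.1209 + 0.2150 = 38.2%.

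| True rate p | q = 0 | q = 10% | q = 20% | q = 30% |
|---|---|---|---|---|
| 50% | 17% | 27% | 38% | 51% |
| 60% | 5.5% | 11% | 21% | 33% |
| 70% | 1% | 4% | 9% | 19% |

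**3. Arm B size.** At p = 70% the table intends 14 patients. The chance of landing in the 30-patient row, P(4 ≤ X ≤ 6), is 34%, 50%, 62% and 66% at q = 0, 10%, 20% and 30%.

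**4. Between-arm t-test (Section 9.3).** Let δA and δB be the mean changes among inhibited tumors, and let a failed tumor contribute a change near zero. The expected difference in means is (1 − qA)δA − (1 − qB)δB.

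- Equal failure q: (1 − q)(δA − δB). This is diluted, and zero when Letrozole has no effect.
- No Letrozole effect, δA = δB = δ: (qB − qA)δ. This is non-zero only if failure differs by arm.

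The documents give no standard deviation for the change, so the t-test's error rate cannot be computed. As an indication only, the chi-squared test used for sizing (10 vs 14, 70% in both arms) rejects as follows:

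| Failure A / B | Rejection |
|---|---|
| 0 / 0 | 4.6% |
| 10% / 10% | 5.1% |
| 20% / 20% | 5.5% |
| 10% / 20% | 6.8% |
| 10% / 30% | 11% |
| 10% / 40% | 19% |

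With 30% failure in both arms, power on the same scale falls from 80% to 59% (60% vs 15%, 10 vs 30) and from 93% to 66% (80% vs 15%, 10 vs 14).

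**5. Cost of replacement.** Tumors needed for 10 scored = 10/(1 − q), rounded up: 11.1 → 12, 12.5 → 13 and 14.3 → 15 at q = 10%, 20% and 30%.

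**The case against.** The best defence is that the protocol already looks for the problem. The mTORC1 markers are on the blot, phospho-S6 is stained with a center-versus-edge check, and Arm B waits on successful molecular analyses. An investigator facing X ≤ 3 could inspect these before interpreting the result. That stands as far as interpretation goes. It does not change the rule, which ends the study on the phospho-AKT count alone.

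A reader might infer that failed cores would pass for a Letrozole effect. The documents do not support this as it stands. The binary score is described as a sizing metric, and the planned test in Section 9.3 averages changes. Section 5.2.2 takes Arm B tissue by the same procedure as Arm A, and nothing in the text predicts more failures there. Equal failure leaves the false-positive rate near 5%, and the 19% figure needs 10% against 40%. Unequal failure is possible, because the arms run one after the other without randomization, but that is as far as the text goes.

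A reader might also take the 1-hour against 24-hour contrast as evidence of poor drug delivery. It bears at least as much on whether AKT feedback has had time to develop, and Section 5.5.1 reserves longer cultures of spare cores for delayed changes. The cell-line data say nothing about penetration into cores.

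Two further objections stand. The existing replacement rule covers tissue amount and cellularity, not assay failure. And selecting tumors on a marker read after RAD001 could select differently by arm if Letrozole itself lowers mTORC1 signaling. This argues against applying the condition to the primary between-arm test.

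**Conclusion.** The point holds for the use of X in Section 9.6. As written, tumors without confirmed mTORC1 inhibition count toward termination and toward a larger Arm B. Under the assumptions above, 20% failure raises the chance of stopping from 17% to 38% at a true rate of 50%, and from 1% to 9% at 70%. At 10% failure the figures are 27% and 4%. Every failure rate is assumed, and so is the absence of any phospho-AKT rise in failed tumors; if some failed tumors crossed the 50% threshold, the increases would be smaller. The 17% at zero failure comes from having ten tumors and is not part of this point.

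For Section 9.3 the conclusion is narrower. Equal failure costs power, and a spurious Letrozole effect arises only if failure is more frequent in Arm B. The documents neither show nor exclude that.

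**What to change.** In Section 9.6, count X only among Arm A tumors whose RAD001 cores show a fall in phospho-p70S6K-Thr389 or phospho-S6-Ser240/244 relative to their own DMSO cores. Name the marker and fix the cut-off before phospho-AKT is read; the documents give no basis for a value, so the laboratory must set it. Then choose one of two routes:

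- Extend the Section 5.4 replacement rule to assay failure, so that ten inhibited tumors are scored. P(stop) then returns to the q = 0 column.
- Read X as a fraction of inhibited tumors, and restate the table in proportions. Otherwise a result such as 3 of 8 (37.5%) falls between the stop row (up to 30%) and the next row (from 40%).

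Report the all-tumor count alongside in either case.

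In Section 9.3, keep the all-tumor t-test as primary. Report the proportion of tumors with confirmed mTORC1 inhibition by arm, and add the comparison among inhibited tumors as a pre-specified sensitivity analysis.

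The markers are already measured, so no new assay is needed. Replacement costs about 12 to 15 Arm A tumors for 10 scored at 10% to 30% failure; the fraction route costs a smaller denominator for X. The change does not settle whether 1 hour is long enough for AKT feedback to appear: a tumor with phospho-S6 down and AKT not yet up would still be scored as non-activated.

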10. HUMAN SUBJECTS
  - 10.1 Subject patient population

Patients with potentially resectable Stage I-III biopsy-proven ER+/HER2- breast cancer.

#### 10.2 Consent Procedures

Patients must give a statement of informed consent. The informed consent must be approved by the Committee for the Protection of Human Subjects at Dartmouth College, the Dartmouth-Hitchcock Medical Center IRB. Before initiating a trial, the investigator will have written and dated approval from the CPHS of Dartmouth-Hitchcock Medical Center for the trial protocol, amendment(s), written informed consent form, consent form updates, subject recruitment procedures (e.g., advertisements) and written information to be provided to subjects. The investigators, or a person designated by the investigators, will explain the benefits and risks of participation in the study to each subject (and impartial witness when applicable) and obtain written informed consent prior to the subject entering the study (before initiation of non-routine tests and administration of study drug). The final form must be agreed to by the CPHS of Dartmouth-Hitchcock Medical Center and must contain all elements in the sample form, in language readily understood by the subject. Each subject's original consent form, signed and dated by the subject and by the person who conducted the informed consent discussion, will be retained by the investigator. In addition, a copy of the signed informed consent will be given to the subject.

#### 10.3 Potential Risks and Benefits

The physical risk of study participation is low. Subjects in Arm A are receiving no study-related treatment. Subjects in Arm B are receiving 10-21 days of treatment with 2.5 mg/day Letrozole prior to surgery; adjuvant therapy with this drug and dose are standard-of-care for this patient population, and will be administered for up to 5 years after surgery. The results of this investigation may provide novel information on ER and PI3K/mTOR signaling pathways in breast cancer, which may shape the development of future treatment regimens to benefit future patients with breast cancer. Loss of patient confidentiality is a risk of participation. Participation in this study is of low overall risk and has no potential for direct clinical benefit.

#### 10.4 Confidentiality

The pathology specimens from the patient biopsies will be labeled only with the patient case number. The key matching patient identification with the patient case number will be kept in a locked drawer in the PI's office. Only the PI and his designated representatives will have access to this key. No one will have access to the study records but for the Investigators and CRA's, the Dartmouth-Hitchcock CPHS, the FDA, and OPRR.

